**Section 11.1 Primary Endpoint – Mean Change in Hb from Pre-treatment to the End of the Primary Efficacy Period (Week 6)**

**The primary objective of this study is to evaluate the dose-response relationship between oral vadadustat once daily dosing for 6 weeks and the change in Hb in Japanese subjects with anemia secondary to DD-CKD; in order to define the starting dose for use in Phase 3 clinical studies in Japan.**

**The primary endpoint is the mean change in Hb from pre-treatment to the end of the primary efficacy period (Week 6). Pre-treatment Hb is defined as the average of 3 Hb values obtained prior to treatment based on the 2 qualifying screening Hb value and the Hb value at the baseline visit.**

**Section 11.2 Primary Efficacy Analysis and Sample Size Determination**

**An analysis of covariance (ANCOVA) model will be used to compare change from pre-treatment in Hb between the 3 vadadustat dosing groups and the placebo group. The model will include treatment assignment (3 dosed groups and 1 placebo group) and pre-treatment Hb value as a covariate. A step-down procedure will be used to control the overall type I error rate for the multiple comparisons. Testing of the highest dose compared with placebo will be conducted first. If and only if this comparison is significant, then testing will proceed to comparison of the next lower dose and placebo, and so on. As a result, no multiplicity adjustment will be needed for this analysis.**

**The study is powered based on a comparison of the highest dose vadadustat group (600 mg daily) and the placebo group.**

**Based on the results from Study AKB-6548-CI-0005 that was conducted in the United States and evaluated vadadustat in patients with anemia secondary to NDD CKD, it is assumed that the expected mean Hb changes from pre-treatment to Week 6 will be approximately 0 mg/dL for the placebo group and 1.35 g/dL for the highest dose vadadustat group (600 mg daily).**

**Based on the results from Study AKB 6548 CI 0011 that was conducted in the United States and evaluated vadadustat in patients with anemia secondary to DD-CKD, it is assumed that the common Hb standard deviation will be 0.9 g/dL across treatment groups. In addition, a dropout rate of 10% is assumed. With these assumptions, the study with n=12 subjects per group will have >85% power to detect the difference between treatment group and control group, at 2-sided alpha of 0.05.**

*Text deleted from Section 11:*

~~The primary objective of this study is to quantify the dose-response relationship between oral vadadustat once-daily dosing for 6 weeks and change in Hb in Japanese subjects with DD-CKD in order to define the starting dose for use in Phase 3 clinical studies in Japan.~~

~~Change in Hb is defined as the Hb measured at the Week 6 visit minus the mean pre-treatment Hb. Note that a pre-treatment average value for Hb is defined as the average of 3 values obtained prior to dosing, ie, the 2 qualifying screening values and the baseline value.~~

~~Linear regression analysis will be used to calculate the relationship between vadadustat dose and change in Hb.~~

[figure not shown]
[figure not shown]

~~The primary analysis will use a linear regression analysis to quantify the association between vadadustat dose and mean change in Hb (ie, to assess the vadadustat dose-response relationship). Comparison of each vadadustat dose group versus will be performed. All tests of significance will be performed using a 0.05 two-sided significance level.~~

~~Based on the results from Study AKB-6548-CI-0005 that was conducted in the United States and evaluated vadadustat in patients with anemia secondary to NDD-CKD, the expected mean Hb changes from baseline to Week 6 will be 0, 0.5, 0.7, and 1.2 g/dL for the placebo, 150 mg, 300 mg, and 600 mg vadadustat dose groups, respectively, with a common standard deviation of 0.68 g/dL among the 4 treatment groups. With these assumptions, the study will have >85% power to detect a non-zero slope in a dose-response relationship using linear regression analysis and  $\alpha=0.05$ , based on simulation of 10,000 repetitions using SAS® software, Version Number 9.4.~~

11.4.1, Analysis Populations for the Safety Analyses
	
The intent-to-treat (ITT) population will include all subjects assigned to study medication who receive at least 1 dose of study medication. All safety analyses will be performed using the ITT population.
	
The <del>intent to treat (ITT)</del> safety population is defined as <del>will include all enrolled</del> subjects assigned to study medication who receive at least 1 dose of study medication. The safety population will be based on the actual treatment that patients received. All safety analyses will be performed using the <del>ITT</del> safety population.
	
The various study populations were defined.

11.4.2, Analysis Populations for the Efficacy Analyses
	
The modified intent-to-treat (MITT) population will include subjects who receive at least 1 dose of study medication, have a pre-treatment Hb
	
The modified intent-to-treat (MITT) population is defined as all randomized subjects who receive at least 1 dose of study medication, have a
	
The various study populations were defined.

	
average defined as the average of the qualifying screening value and the baseline value, and at least one post-baseline Hb measurement.
 
The per-protocol (PP) population will consist of the subjects in the MITT population who have completed the study and have efficacy data through Week 6, have a study medication compliance of <math>\geq 80\%</math>, and do not have any major protocol deviations.
	
pre-treatment Hb average defined as the average of the qualifying screening value and the baseline value, and at least one post-baseline Hb measurement. The MITT population will be based on the treatment to which patients are randomized.
 
The per-protocol (PP) population will consist of the subjects in the MITT population who have completed the study and have efficacy data through Week 6, have a study medication compliance of <math>\geq 80\%</math>, and do not have any major protocol deviations expected to significantly affect the primary efficacy endpoint. Subjects with major protocol deviations expected to significantly affect the primary efficacy endpoint will be identified and documented prior to data unblinding.
	

11.5 Efficacy and PD Analyses
	
The entire set of efficacy outcomes will be defined in the statistical analysis plan (SAP). In addition to the primary endpoint analysis defined above, the following efficacy endpoints will also be assessed:
 
 
• Actual values and change (absolute and percent) from baseline in Hb, HCT, RBC count, and reticulocyte count (both absolute and percent)
 
• Actual values and change (absolute and percent) from baseline in iron, TIBC, TSAT, ferritin (both absolute and percent), and hepcidin
 
	
This section has been deleted
	
Editorial revision to focus protocol on statistical approach to primary efficacy analysis. Details related to all planned analyses will be provided in the statistical analyses plan as mentioned in the newly added paragraph at the beginning of Section 11.

	
Changes from baseline of efficacy and PD parameters will be summarized using descriptive statistics by treatment groups and each scheduled assessment, and results will be displayed using box lots.
 
Linear regression analysis will be performed for Hb change from baseline to Week 6, to quantify the association between vadadustat dose and mean change in Hb (ie, to assess the vadadustat dose response relationship).. Comparison of each vadadustat dose group versus baseline will be performed. All tests of significance will be performed using a 0.05 two sided significance level. Similar analysis will be performed for change from baseline to Week 6 of reticulocyte count (both absolute and percent), hematocrit, and RBC count.
 
Also, similar linear regression analysis will be performed for change from baseline to Week 6 of the iron indices (ie, iron, TIBC, ferritin, and TSAT) and hepcidin will be evaluated.
 
All tests of significance will be performed using a 0.05 two sided significance level.
		
11.7, Safety Analyses	The following variables are the safety endpoints: adverse events, vital signs, ECGs, components of the CBC, and VEGF.	The following variables are the safety endpoints: adverse events, vital signs, ECGs, and laboratory parameters <del>components of the CBC, and VEGF.</del>	Editorial revision
11.7, PK Analyses	At the Week 4 visit, pre-dose plasma concentrations of vadadustat and its metabolites will be obtained to evaluate for accumulation of study medication.	This section has been deleted	Editorial revision to focus protocol on statistical approach to primary efficacy analysis. Details related to all planned analyses will be provided in the

		
statistical analyses plan as mentioned in the newly added paragraph at the beginning of Section 11.


18, Appendices
	
Appendix C: Definitions of ESA Status Inclusion Criteria and ESA Washout Period, was added to provide additional clarity regarding when subjects are to washout ESA therapy.
 
Subjects who are not being treated with ESAs:
 
Example 1:      ESA use      No prior ESA use                           ESA washout      No ESA washout required
  
Example 2:      ESA use      [Redacted]      Last ESA dose before SV1 ≥2w for epoetin alfa, beta, or kappa; ≥4w for darbepoetin alfa; or ≥8w for epoetin beta pegol                           ESA washout      No ESA washout required
  
Subjects who are being treated with ESAs:
 
Example 1:      ESA use      [Redacted]      Last ESA dose before SV1 <2w for epoetin alfa, beta, or kappa; <4w for darbepoetin alfa; or <8w for epoetin beta pegol                           ESA washout*      [White box]
  
Example 2:      ESA use      [Redacted]                           ESA washout*      [White box]
  
*After SV1 and before SV2, ≥2w off of epoetin alfa, beta, or kappa; ≥4w off of darbepoetin alfa; or ≥8w off of epoetin beta pegol
	

---

## NOTE TO FILE

---

**Protocol Number:** AKB-6548-CI-0022

**Protocol Title:** Phase 2, Randomized, Double-Blind, Placebo-Controlled, Dose-Finding Study to Assess the Efficacy, Safety, Pharmacokinetics, and Pharmacodynamics of Vadadustat in Japanese Subjects with Anemia Secondary to Chronic Kidney Disease (DD-CKD)

**Protocol Section:** 9.1 – Schedule of Events, **Appendix B** – Schedule of Activities for Subjects Who Were Prescribed ESAs Prior to Study Entry (ESA Washout is Required)

**Subject:** Clarification regarding administrative errors

**Date:** 16-Dec-2016

---

This is to confirm that the below editorial changes will be made to the English version of protocol AKB-6548-CI-0022 (v.2.0, 23Nov2016) at the time of the next protocol amendment. Please note that these edits were made in the Japanese version of the protocol.

**Section 9.1 – Schedule of Events:** Day 42 will be updated to Day -42.

- For subjects who were prescribed epoetin alfa, epoetin beta, and epoetin kappa prior to study entry, the screening visits must be performed within 6 weeks (Day 42 to Day 0) prior to dosing on Day 1. There will be a 2-week ESA washout period between screening visit 1 and screening visit 2, in addition, screening visit 2 after the  $\geq 2$ -wk ESA washout; screening visit 3 should be  $\geq 4$  days from screening visit 2; and baseline visit (Day 1) should be  $\geq 4$  days from screening visit 3.

**Appendix B: Schedule of Activities for Subjects who were Prescribed ESAs Prior to Study Entry (ESA Washout is Required):** A [c] will be added after Serum Pregnancy test in the Schedule of Events.

(ESA washout and RBC transfusion) review				
Serum pregnancy test	X		X	
Iron indices	X			X
Folate and	X			

- [b] SAEs that are deemed by the investigator to be related to protocol procedures (eg, ESA washout) must be reported after signing of the informed consent form. The reporting period for all non-serious AEs and all SAEs not related to protocol procedures begins upon receiving the first dose of study medication and ends at the final protocol-required visit.
- [c] In the event screening visit 3 is >8 days prior to Day 1, the subject will be asked to return to the study site for an unscheduled serum pregnancy test to verify eligibility prior to Day 1.

Printed Name: \_\_\_\_\_ Role: \_\_\_\_\_

Signature: \_\_\_\_\_ Date: 16-Dec-2016

---

## NOTE TO FILE

---

**Protocol Number:** AKB-6548-CI-0022

**Protocol Title:** Phase 2, Randomized, Double-Blind, Placebo-Controlled, Dose-Finding Study to Assess the Efficacy, Safety, Pharmacokinetics, and Pharmacodynamics of Vadadustat in Japanese Subjects with Anemia Secondary to Dialysis Dependent Chronic Kidney Disease

**Subject:** Administrative errors in Protocol Version 2.0 and Summary of Changes (SOC)

**Date:** 03 February 2017

---

This is to clarify that the following administrative errors were noted in Protocol version 2.0 and the corresponding Summary of Changes (SOC) document, dated 23 November 2016.

- **The following highlighted text the protocol synopsis, protocol section 11.2, and the SOC, is incorrect: “mg/dL” should be “g/dL”**
  - *Based on the results from Study AKB-6548-CI-0005 that was conducted in the United States and evaluated vadadustat in patients with anemia secondary to NDD-CKD, it is assumed that the expected mean Hb changes from baseline to Week 6 will be approximately 0 mg/dL for the placebo group and 1.35 g/dL for the highest dose vadadustat group (600 mg daily), with a common standard deviation of 0.68 g/dL across treatment groups.*

**Printed Name:** \_\_\_\_\_ **Role:** Clinical Project Manager \_\_\_\_\_

**Signature:** \_\_\_\_\_ **Date:** \_\_\_\_\_

Q3	3rd quartile
RBC	red blood cell
SAE	serious adverse event
SAP	statistical analysis plan
SD	standard deviation
SMQ	standardised MedDRA queries
SOC	system organ class
TEAE	treatment-emergent adverse event
TIBC	total iron binding capacity
TSAT	transferrin saturation
TTR	time in therapeutic range
uACR	urine albumin-to-creatinine ratio
VEGF	vascular endothelial growth factor

1 INTRODUCTION

This study is a Phase 2 clinical study to assess the dose-response relationship between oral vadadustat once daily dosing for 6 weeks and the change in hemoglobin (Hb) in Japanese subjects with anemia secondary to dialysis dependent chronic kidney disease (DD-CKD); in order to define the starting dose for use in Phase 3 clinical studies in Japan.

This Statistical Analysis Plan (SAP) defines the preliminary and final statistical analyses for the clinical study report for this study. This should be read in conjunction with the study protocol that provides all necessary background information and rationale for the current study and its design.

The pharmacokinetic data will be separately obtained from vendor to keep blindness of the study.

This SAP is based upon the following study documents:

- Study Protocol, Version 2 (November 23, 2016)
- electronic Case Report Form (eCRF), Version 2.0 (January 27 2017)
- Protocol Deviation Specification Form, Version 2.0 (February 07, 2017)

2 STUDY OBJECTIVES

2.1 Primary Objective and Endpoint

The primary objective of this study is to assess the dose-response relationship between oral vadadustat once daily dosing for 6 weeks and the change in Hb in Japanese subjects with anemia secondary to DD-CKD; this is to define the starting dose for use in Phase 3 clinical studies in Japan.

The primary endpoint that will be used to assess this objective is the mean change in Hb levels from pre-treatment to the end of the primary efficacy period (Week 6). Pre-treatment Hb is defined as the average of 3 Hb values obtained prior to treatment based on 2 qualifying screening Hb values and the Hb value at the baseline visit (Day 1).

2.2 Secondary Objectives and Endpoints

The secondary objectives of this study are:

- To assess the safety, tolerability, pharmacokinetics (PK), and pharmacodynamics (PD) of oral vadadustat once daily dosing in Japanese subjects with anemia secondary to DD-CKD during the 6-week, primary efficacy period
- To evaluate the effect of dose adjustments and demonstrate the maintenance effect on Hb during a 10-week dose-adjustment and maintenance period
- To assess the time to reach the target Hb range from baseline

The secondary endpoints that will be used to assess these objectives include the following:

- Time to reach target Hb level of 10.0-12.0 g/dL from baseline visit (Day 1)
- Mean Hb levels at the end of the primary efficacy period (Week 6) and at the end of the dose adjustment and maintenance period (Week 16)
- Proportion of subjects who achieve target Hb 10.0-12.0 g/dL at the end of the dose adjustment and maintenance period (Week 16)
- Mean change in Hb between pre-treatment and the end of the dose adjustment and maintenance period (Week 16)
- Mean change in hematocrit, red blood cell (RBC) count, and reticulocyte count from baseline to the end of the primary efficacy period (Week 6) and the end of the dose adjustment and maintenance period (Week 16)
- Mean change in iron indices (i.e., iron, total iron-binding capacity [TIBC], transferrin saturation [TSAT], and ferritin) and hepcidin from baseline to the end of the primary efficacy period (Week 6) and the end of the dose adjustment and maintenance period (Week 16)
- Proportion of subjects requiring rescue with RBC transfusion from baseline to the end of the primary efficacy period (Week 6) and the end of the dose adjustment and maintenance period (Week 16)
- Proportion of subjects requiring rescue with erythropoiesis-stimulating agents (ESAs) from baseline to the end of the primary efficacy period (Week 6) and the end of the dose adjustment and maintenance period (Week 16)
- Number of dose adjustments from baseline to the end of the dose adjustment and maintenance period (Week 16)
- Plasma concentration profile of vadadustat and its metabolites using pre-dose sample from Week 4

The safety endpoints that will be used to assess these objectives include the following:

- Safety assessments, including adverse events (AEs), vital signs, electrocardiograms (ECGs), and other laboratory assay results (eg, chemistry, components of the complete blood count [CBC] other than the ones noted above, and vascular endothelial growth factor [VEGF])

3 INVESTIGATIONAL PLAN

3.1 Overall Study Design and Plan

[figure not shown]
This is a Phase 2, randomized, double-blind, placebo-controlled, dose-finding study to assess the efficacy, safety, tolerability, PK, and PD of orally administered vadadustat in Japanese subjects with anemia secondary to DD-CKD. The study does not include a pre specified male to female ratio.

Approximately 48 subjects will be enrolled at approximately 35 sites in Japan.

There will be around 12 subjects enrolled in each of the 4 treatment groups . Please see the protocol section 8.2.2 for information regarding the randomization scheme.

An overview of the study design is presented in Figure 1.

Figure 1: Overview of Study Design

The study will include the following periods:

- Eligibility screening period (up to 4 weeks)
 - Up to 4 weeks for subjects who were not prescribed ESAs prior to study entry (Day -28 to Day 0)
 - Up to 6 weeks for subjects who were prescribed epoetin alfa, epoetin beta, and epoetin kappa prior to study entry (Day -42 to Day 0)
 - Up to 8 weeks for subjects who were prescribed darbepoetin alfa prior to study entry (Day -56 to Day 0)
 - Up to 11 weeks for subjects who were prescribed epoetin beta pegol prior to study entry (Day -77 to Day 0)
- Primary efficacy period (6 weeks; Weeks 1 to 6)
- Dose adjustment and maintenance period (10 weeks; Weeks 7 to 16)
- Follow-up period (2 weeks; Weeks 17 and 18)

Subjects will participate in a screening period to determine study eligibility. Subjects who have not recently received ESA therapy will participate in 2 screening visits. Subjects who have recently received ESA therapy and otherwise meet eligibility criteria

will be required to washout from ESA therapy prior to evaluation of screening Hb, and will participate in 3 screening visits.

Eligible subjects will be randomized following the screening period using a central randomization system. Subjects will be randomized 1:1:1 to receive 1, 2, or 4 tablets at their baseline visit (Day 1). Within each tablet-count group, subjects will be randomized 3:1 to receive vadadustat (150, 300, or 600 mg vadadustat) or placebo.

Study drug treatment will be administered during a 6-week primary efficacy period. See the protocol section 8.2.4 for information on study drug administration. The primary efficacy period includes fixed-dose treatment to establish a dose-response relationship. However, if Hb level increase rapidly or if the Hb levels exceeds 13.0 g/dL, the study drug dose can be decreased or interrupted (see the protocol section 8.2.4).

After completing the primary efficacy period, subjects will continue to a 10-week dose adjustment and maintenance period (see the protocol section 8.2.5). Subjects receiving placebo will be switched to vadadustat, and study drug dose will be adjusted to achieve a target Hb of 10.0-12.0 g/dL based on dose adjustment guidelines (see the protocol section 8.2.5).

Vadadustat treatment will stop after the dose adjustment and maintenance period has been completed (Week 16) and subjects will continue in a 2-week follow-up period (Week 17-18).

For subjects who were not being treated with ESAs, the clinical and safety assessments will be performed as described in the protocol section 9.4 and as listed in the protocol Appendix A. For subjects who were being treated with ESAs prior to study entry, the clinical and safety assessments will be performed as described in the protocol section 9.5 and as listed in the protocol Appendix B.

3.2 Efficacy and Safety Variables

3.2.1 Efficacy and PD Variables

The following variable is the primary efficacy variable:

- Change from pre-treatment in Hb at Week 6.

The following efficacy endpoints will also be analyzed:

- Actual values and change (absolute and percent) from baseline in Hb, hematocrit, RBC count, and reticulocyte count (both absolute and percent)
- Actual values and change (absolute and percent) from baseline in iron, TIBC, TSAT, ferritin, and hepcidin

3.2.2 Safety Variables

The following variables are the safety endpoints:

- AEs
- Vital signs
- ECGs
- Laboratory parameters

3.2.3 PK Variables

The following variables are the PK variable:

- Pre-dose plasma concentrations of vadadustat at the Week 4 visit
- Pre-dose plasma concentrations of vadadustat's metabolites at the Week 4 visit

4 STATISTICAL METHODS

4.1 Data Quality Assurance

All tables, figures and data listings to be included in the report will be independently checked for consistency, integrity and in accordance with standard PAREXEL procedures.

4.2 General Presentation Considerations

Pre-treatment Hb is defined as the average of 3 Hb values obtained prior to treatment based on most recently 2 qualifying screening Hb values and the Hb value at the baseline visit (Day 1). 'Pre-treatment' for other variables is defined as the last available pre-treatment assessment. In general, this is the value at the Baseline Visit. 'End of Treatment (EOT)' is defined as the assessment on the EOT form labeled as 'Week 16 Visit', even if other values closer to Day 113 are available. For the analysis purpose, only actual visit will be used and hence EOT will be presented as "Week 16". In the summary table, EOT of early withdrawal will not be counted but only be displayed in the listing for reference purpose. 'Treatment Day' will be calculated relative to start of dosing at Baseline Visit (i.e. Treatment Day = Assessment Date - Baseline Visit Date + 1).

Continuous data will be summarized in terms of the mean, standard deviation (SD), median, minimum, maximum and number of observations, unless otherwise stated. The minimum and maximum will be reported to the same number of decimal places as the raw data recorded in the database. The mean and median will be reported to one more decimal place than the raw data recorded in the database. The SD will be reported to two more decimal places than the raw data recorded in the database. In general, the maximum number of decimal places reported shall be four for any summary statistic.

Categorical data will be summarized in terms of the number of subjects providing data at the relevant time point (n), frequency counts and percentages. Any planned collapsing of categories will be detailed in the SAP text and the data displays.

Percentages will be presented to one decimal place. Percentages will not be presented for zero counts. Percentages will be calculated using n as the denominator. If sample sizes are small, the data displays will show the percentages, but any textual report will describe frequencies only.

Changes from baseline in categorical data will be summarized using shift tables where appropriate.

P-values greater than or equal to 0.001, in general, will be presented to three decimal places. P-values less than 0.001 will be presented as “<0.001”.

Confidence intervals will be presented to one more decimal place than the raw data.

All report outputs will be produced using SAS® version 9.3 or a later version in a secure and validated environment. All report outputs will be provided to the Sponsor in a single Microsoft Word 2010 [Version 14.0] document.

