4.3 Study Subjects

4.3.1 Disposition of Subjects

A clear accounting of the disposition of all subjects who enter the study will be provided, from screening to study completion.

The summary of the following subject disposition will be presented.

- A summary of the number of subjects randomized, the number and percentage of subjects treated (with at least one dose of study medication) and the number and percentage of subjects completed through Week 6 Visit and discontinued by Week 6 Visit by treatment group and overall (Analysis population: All Subjects Randomized). For final analysis, a summary of the number and percentage of subjects completed Week 18 Visit and discontinued from the study by treatment group and overall will be provided (Analysis population: All Subjects Randomized). Withdrawals from the study will also be summarized by major reason.

By-subject listings of eligibility details, randomization details, visit dates and withdrawal/study completion details (including reason for discontinuation and duration of treatment prior to discontinuation) will be provided.

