4.4 Analysis Populations

Upon database release, protocol deviation and analysis population outputs will be produced and will be sent to Sponsor for review. An analysis population classification meeting will be arranged to discuss the outputs and to decide which subjects and/or subject data will be excluded from certain analyses. Decisions made regarding the exclusion of subjects and/or subject data from analyses will be made prior to unblinding and will be documented and approved by Sponsor.

The following summary of analysis population will be provided:

- A summary of the number and percentage of subjects allocated to each analysis population by treatment group and overall (Analysis population: All Subjects Randomized)

A by-subject listing of analysis population details will be provided. This listing will be presented by treatment group and include: site, subject identifier, inclusion/exclusion flag for each population and reason for exclusion from each population. All subjects randomized will appear on this listing.

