4.4.2 Analysis Populations for the Efficacy Analyses

The efficacy summaries and analyses will be based on the **modified intent-to-treat (MITT) population**. The MITT population is defined as all randomized subjects who have received at least 1 dose of study medication and have a pre-treatment Hb average defined as the average of the most recently 2 qualifying screening value and the baseline value, and at least one post-baseline Hb measurement. **The post-baseline Hb measurement will exclude the withdrawal Hb and follow-up Hb measurements for discontinued patients.** In the event that a subject is allocated the incorrect study treatment as per the study randomization list, subjects will be summarized and analyzed ‘as randomized’ i.e. by randomized treatment group.

For the efficacy variables, sensitivity analyses will be performed on the **per-protocol (PP) population** to assess the robustness of the study conclusions to the choice of analysis population. The PP population is defined as the subjects in the MITT population who have completed the study and have efficacy data through Week 6, have a study medication compliance of $\geq 80\%$, and do not have any major protocol deviations expected to significantly affect the primary efficacy endpoint. Subjects with major protocol deviations expected to significantly affect the primary efficacy endpoint will be identified and documented prior to data unblinding.

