4.7.1.3 Handling of Missing Data

For the MITT population analyses for the primary efficacy variable, the Last Observation Carried Forward (LOCF) approach will be used to impute missing data for primary efficacy analysis.

Subjects who underwent dose reduction before week 6 will not be analyzed differently from subjects who did not undergo dose reduction. This means we will use the actual Hb at week 6 for all subjects except the missing data, which will be carried from the last Hb before week 6 and after baseline.

- If a Baseline value is missing, the last value prior to baseline will be carried forward to the Baseline value but not to further values during the treatment period.
- For post-Baseline assessments, hemoglobin measurements at end of treatment and follow-up visits are not carried forward. Other than that, the most recent post-baseline assessments to the primary evaluation period (week 6) will be carried forward. Baseline and pre-Baseline values will not be carried forward to the post-Baseline visits.

For the secondary endpoint analyses, data will be used as observed and no imputation method will be used.

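### Subjects discontinued for rescue or worsening anemia leave the denominator of the Week 16 target-Hb percentage, and of the Week 6 target-range tests if lost before Week 6

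*SAP*

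**What the plan says.** - **Denominator.** For categorical data, SAP 4.2 reports "the number of subjects providing data at the relevant time point (n"), then counts and percentages. It adds: "Percentages will be calculated using n as the denominator".
- **Early withdrawals.** Protocol 7.6.3 asks a subject who stops early to have the Week 16 (EOT) assessments at about the time of stopping. SAP 4.2 sets that value aside: "In the summary table, EOT of early withdrawal will not be counted but only be displayed in the listing for reference purpose".
- **Missing data.** SAP 4.7.1.3 confines LOCF to the primary variable. For the rest: "For the secondary endpoint analyses, data will be used as observed and no imputation method will be used".
- **Rescue.** Under Protocol 8.2.6, starting ESA rescue or a red cell transfusion ends both study drug and study participation. Protocol 7.6.2 lists worsening anemia needing either one as a discontinuation reason.
- **Measures affected.** Protocol 5.2 makes the proportion in the 10-12 g/dL range at Week 16 a secondary endpoint. SAP 4.7.3 summarizes it by treatment group and adds Fisher's exact tests of the Week 6 proportion, each dose against placebo. It gives no other denominator and no non-responder rule.
- **Rescue count.** SAP 4.7.3 counts an ESA rescue only when four criteria hold together: ESA was given; it was given for worsening anemia or symptoms; it was given because Hb was below 9.0 g/dL; and the recorded withdrawal reason is the one for worsening anemia. A separate row counts all ESA administration.

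**The concern.** In this trial missingness is partly defined by failure: a subject whose anemia worsens enough to need rescue is removed by design. A proportion computed only on subjects still present then answers a narrower question than the protocol's endpoint, namely how many of those who stayed were in range. An arm that loses its worst responders is not marked down for losing them.

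The SAP is also uneven at Week 6. An MITT subject rescued after a Week 2 or Week 4 Hb is kept in the primary analysis through LOCF, yet is absent from the target-range test at the same visit.

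A smaller counting mismatch concerns the ESA-rescue endpoint. The SAP's four criteria are narrower than the conditions under which Protocol 8.2.6 allows rescue, so some protocol-permitted rescues can go uncounted.

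**Working it through.** The documents give no expected rescue rate or target-range rate, so there is no plan figure to reproduce. Inputs from the documents are 12 subjects per group and 10% dropout (Protocol 11.2). All responder and loss counts below are illustrative assumptions.

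**1. Tracing one subject.** ESA rescue at Week 5 → discontinued (Protocol 8.2.6) → no scheduled Week 6 or Week 16 Hb → withdrawal Hb not counted (SAP 4.2) → no imputation (SAP 4.7.1.3) → not in n. The subject is in neither part of either proportion. If rescued after the Week 6 sample, the subject counts at Week 6 and is lost only at Week 16. The PP analysis does not repair this, since PP requires efficacy data through Week 6 (SAP 4.4.2).

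**2. Size of the shift.** Let N be the MITT subjects in an arm, n those with data and k those in range. The reported share is k/n. Counting missing subjects as not in range gives k/N. The ratio is N/n.

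| Missing, of 12 | N/n |
|---|---|
| 1 | 12/11 = 1.09 |
| 2 | 12/10 = 1.20 |
| 3 | 12/9 = 1.33 |
| 10% dropout (12 × 0.9 = 10.8) | 12/10.8 = 1.11 |

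At 10% dropout, 4/12 = 33% becomes 4/10.8 = 37%, 6/12 = 50% becomes 56%, and 8/12 = 67% becomes 74%.

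The sign depends on the missing subject. If that subject would have been in range, the full share is 7/12 = 58% against a reported 6/11 = 55%.

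**3. Week 6 Fisher test.** I enumerated all tables with 12 per arm and more in range on active than on placebo, removed non-responders, and counted how often the two-sided p-value crosses 0.05.

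| Lost: active / placebo | Tables crossing | Direction |
|---|---|---|
| 1 / 1 | 1 of 66 | gains significance |
| 1 / 0 | 8 of 66 | all gain |
| 0 / 1 | 0 of 78 | none |
| 0 / 2 | 4 of 77 | all lose |

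Example: 8/12 v 3/12 gives p = 0.100. Losing one active non-responder (8/11 v 3/12) gives p = 0.039. Losing one from each arm (8/11 v 3/11) gives p = 0.086.

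With binomial weights (assumed true shares 50-80% on active and 10-30% on placebo), the chance that the conclusion changes is at most 1.6% for 1/1, about 4-18% for 1/0, about 0.1% or less for 0/1, and about 0.5-16% for 0/2.

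**4. Rescue count set against Protocol 8.2.6.**
- *Criterion 4.* Protocol 7.6.2 has the investigator record one primary reason for discontinuation. A rescue recorded under any other reason fails this criterion.
- *Criterion 3.* The protocol lets the investigator start ESA without a confirmatory Hb below 9.0 g/dL if its first two conditions are met, and neither of those contains an Hb threshold. If this waives only the second, confirming value, the SAP's single value agrees with it. If it waives any such value, a permitted rescue fails criterion 3.
- *All-ESA row.* This picks up such cases, because Protocol 8.4.2 bars ESA on study except as rescue. It can also include ESA resumed as standard of care after discontinuation for another reason (Protocol 7.6.3), so it does not replace the rescue count.

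**The case against.** The as-observed rule is explicit and prespecified, and it keeps an off-schedule withdrawal Hb from being counted as a Week 16 success. Failures are not hidden. Rescue has its own rows, disposition is tabulated ("Withdrawals from the study will also be summarized by major reason"), and so are the populations ("A summary of the number and percentage of subjects allocated to each analysis population by treatment group and overall"). With n displayed, a reader can rebuild the all-MITT share. SAP 4.2 also tempers the text: "If sample sizes are small, the data displays will show the percentages, but any textual report will describe frequencies only", though it sets no threshold for small. SAP 4.7.1.4 calls the secondary variables supportive, and the Week 6 target-range test is not among the protocol's endpoints. Counting every missing value as failure has a bias of its own. All of this stands, and it limits the weight of the point. It does not change the fact that the headline percentage ignores subjects removed for failure.

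Three stronger readings are tempting and are not supported:
- *The Week 6 tests are biased toward vadadustat.* Direction depends on which arm loses subjects, which the documents do not determine. When only placebo loses non-responders, the crossings above all lose significance.
- *The ≥1 g/dL responder test has the same fault.* Its summary is cumulative and its test names no visit. MITT membership already requires a post-baseline Hb (SAP 4.4.2), so a subject who leaves without the increase is most naturally a non-responder already. Only the unstated denominator needs confirming.
- *The primary analysis is affected.* It uses LOCF, so the as-observed rule does not reach it. Subjects excluded from MITT altogether are a different matter ("The post-baseline Hb measurement will exclude the withdrawal Hb and follow-up Hb measurements for discontinued patients"), which a change of denominator does not address.

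**Conclusion.** The point holds for the Week 16 target-Hb percentage, and for the Week 6 target-range Fisher tests when the subject is lost before Week 6. Near the planned dropout, the reported percentage is about 1.09 to 1.11 times the all-MITT share, and 1.33 times with 3 of 12 missing, provided missing subjects are taken as not in range. At Week 16 the figure is descriptive, with every arm on vadadustat. At Week 6 the conclusion seldom changes with balanced loss; it can change when loss is lopsided, in either direction. This is a worthwhile, inexpensive correction to a supportive measure and does not threaten the trial's main conclusion.

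The rescue count is a separate and narrower matter: the criterion 4 mismatch arises whenever a site records another primary reason, and the criterion 3 mismatch depends on how the protocol's waiver is read.

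**What to change.** **Target-range measures (SAP 4.7.1.3 and 4.7.3).** Report the Week 6 and Week 16 target-range proportions and the Week 6 Fisher tests on all MITT subjects, counting anyone without an Hb at the visit as not in target. Show the as-observed version alongside. For the cumulative ≥1 g/dL measure, only state that the denominator is MITT.

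**Rescue count (SAP 4.7.3).** Reconcile the four-part definition with Protocol 8.2.6, for counting only. Count every ESA started as rescue, whatever withdrawal reason is recorded, and including ESA started when study drug is stopped for that rescue. Leave out ESA resumed as standard of care after discontinuation for another reason, and keep the four-part count as sensitivity. The rescue therapy review in Protocol 9.3.1 is the natural source; confirm that the CRF records the distinction. When rescue is given does not change.

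**Cost.** SAP wording and one extra version of the affected tables. Reported percentages become lower or stay equal. Unrelated withdrawals, such as transplant or withdrawn consent, and missed samples will also count as failures; the as-observed version shows how much that matters.
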